- Laboratory tests including serum blood urea nitrogen, creatinine, estimated glomerular filtration rate, sodium, potassium, bicarbonate, ALT, AST, alkaline phosphatase, total bilirubin, albumin, hemoglobin, INR, and immunosuppressant level;
- Serum or urine hCG for females of childbearing potential at Follow Up Week 4;
- Hepatitis B surface antigen at Follow Up Week 4;
- Quantitative HCV RNA;
- Concomitant medications of interest including immunosuppressant on follow up week 4;
- Immunosuppressant dose;
- Assessment for AEs on Follow Up Week 4.

Early End of Treatment or Treatment Failure visit

This unscheduled visit will occur if the subject discontinues study drug prior to planned end of treatment for any reason OR the subject has been determined to have viral breakthrough or relapse. This visit must occur within 2 weeks of stopping treatment or recognition of viral breakthrough or relapse. Each visit is anticipated to require 30 minutes of the subject's time. The following events will take place:

- Clinical examination;
- Laboratory tests including serum blood urea nitrogen, creatinine, estimated glomerular filtration rate, INR, sodium, potassium, bicarbonate, ALT, AST, alkaline phosphatase, total bilirubin, albumin, hemoglobin, and immunosuppressant level;
- Quantitative HCV RNA and HCV genotype;
- Testing for HCV resistance associated substitutions;
- Concomitant medications of interest including immunosuppressant;
- Assessment for AEs.

Visit Windows

The study visit windows are +/- 2 days for the day 3 visit, +/- 4 days for the weekly on treatment visits and end of treatment visit, and +/- 10 days for the follow up visits

End of Study Definition

End of study is considered to be completion of the Follow Up Week 24 Visit. Subjects who enter the Virologic Failure Substudy will also follow an additional

Schedule of Assessments for the Virologic Failure Substudy (See Appendix 3a).

Sample Storage

Residual biological samples will be frozen and stored at the individual study sites. No

human genetic testing will be performed without express consent of the study subjects. At the conclusion of this study, these samples may be retained in storage per individual institution policy.

Study Visits for Virologic Failure Substudy

Study visits for the Virologic Failure Substudy may coincide with visits for the main study. When this occurs, laboratory assessments for the main study may also be used for the Virologic Failure Substudy.

Day 1 (The day SOF/VEL/VOX commences)

- First administration of study drug;
- Laboratory tests including serum blood urea nitrogen, creatinine, estimated glomerular filtration rate, INR, sodium, potassium, bicarbonate, ALT, AST, alkaline phosphatase, total bilirubin, albumin, hemoglobin, immunosuppressant level, and quantitative HCV RNA.
- Concomitant medications of interest including immunosuppressant;

On HCV treatment visits

These 3 visits will occur in the outpatient clinic per the schedule of assessments on Week 1, Week 4, and Week 8. It is anticipated that each of these visits will require 30 minutes of the subject's time. The following events will take place:

- Clinical examination;
- Laboratory tests including serum blood urea nitrogen, creatinine, estimated glomerular filtration rate, sodium, potassium, bicarbonate, ALT, AST, alkaline phosphatase, total bilirubin, albumin, hemoglobin, INR, and immunosuppressant level;
- Serum or urine hCG for females of childbearing potential at weeks 4 and 8;
- Quantitative HCV RNA on weeks 1 and 4;
- Hepatitis B surface antigen on week 4;
- Concomitant medications of interest including immunosuppressant;
- Assessment for AEs.

End of HCV treatment visit

This visit will occur at the end of antiviral treatment at the outpatient clinic. It is anticipated to require 30 minutes of the subject's time. The following events will take place:

- Clinical examination;
- Laboratory tests including serum blood urea nitrogen, creatinine, estimated glomerular filtration rate, INR, sodium, potassium, bicarbonate, ALT, AST, alkaline phosphatase, total bilirubin, albumin, hemoglobin, and immunosuppressant level;
- Serum or urine hCG for females of childbearing potential;

- Quantitative HCV RNA;
- Concomitant medications of interest including immunosuppressant;
- Assessment for AEs.

Post-HCV treatment Follow Up visits

These three visits will occur at 4, 12, and 24 weeks after discontinuation of antiviral treatment. Follow Up visits 4 and 12 will take place in the outpatient clinic while Follow Up Week 24 will occur either in the transplant clinic or local laboratory and may also include a telephone call to confirm the dose of the immunosuppressant medications. Each visit is anticipated to require 15-30 minutes of the subject's time. The following events will take place:

- Clinical examination (Follow Up visits 4 and 12 only;)
- Laboratory tests including serum blood urea nitrogen, creatinine, estimated glomerular filtration rate, sodium, potassium, bicarbonate, ALT, AST, alkaline phosphatase, total bilirubin, albumin, hemoglobin, INR, and immunosuppressant level;
- Serum or urine hCG for females of childbearing potential at Follow Up Week 4;
- Hepatitis B surface antigen at Follow Up Week 4;
- Quantitative HCV RNA;
- Concomitant medications of interest including immunosuppressant on follow up week 4;
- Immunosuppressant dose;
- Assessment for AEs on Follow Up Week 4.

Early End of Treatment or Treatment Failure visit

This unscheduled visit will occur if the subject discontinues study drug prior to planned end of treatment for any reason OR the subject has been determined to have viral breakthrough or relapse. This visit must occur within 2 weeks of stopping treatment or recognition of viral breakthrough or relapse. Each visit is anticipated to require 30 minutes of the subject's time. The following events will take place:

- Clinical examination;
- Laboratory tests including serum blood urea nitrogen, creatinine, estimated glomerular filtration rate, INR, sodium, potassium, bicarbonate, ALT, AST, alkaline phosphatase, total bilirubin, albumin, hemoglobin, and immunosuppressant level;
- Quantitative HCV RNA and HCV genotype;
- Testing for HCV resistance associated substitutions;
- Concomitant medications of interest including immunosuppressant;
- Assessment for AEs.

Visit Windows

The study visit windows are +/- 2 days for the day 3 visit, +/- 4 days for the weekly on treatment visits and end of treatment visit, and +/- 10 days for the follow up visits

End of Study Definition

End of the Virologic Failure Substudy study is considered to be completion of the Follow Up Week 24 Visit.

Sample Storage

Residual biological samples will be frozen and stored at the individual study sites. No human genetic testing will be performed without express consent of the study subjects. At the conclusion of this study, these samples may be retained in storage per individual institution policy.

ADVERSE EVENTS AND TOXICITY MANAGEMENT

Definitions

An adverse event (AE) is any untoward medical occurrence in a study subject administered a medicinal product. It does not necessarily have a causal relationship with the treatment. Preexisting events that increase in severity or change in nature during participation in a clinical study are considered AEs.

A serious adverse event (SAE) is defined as an event that results in the following:

- Death;
- Life threatening event in which the subject was at risk of death at the time of the event;
- Inpatient hospitalization or prolongation of existing hospitalization;
- Persistent or significant disability/incapacity;
- A congenital anomaly/birth defect;
- A medically important event or reaction that may jeopardize the subject or may require intervention to prevent one of the other outcomes constituting SAEs.

Safety monitoring

Safety data will be collected for all subjects who sign their confirmation of consent at the end of the consent form and undergo a NAT-positive transplant through 4 weeks after the last dose of study drug. The Principal Investigators will continuously monitor the study for safety. An independent data and safety monitor will act in an advisory capacity to monitor participant safety and data quality, as well as to evaluate the progress of the study.

The lead investigators will be responsible for holding periodic meetings to update the study group regarding enrollment, study conduct, and potential safety issues that may affect subjects' decisions about enrolling or continuing study drug throughout the study, including, but not limited to: AEs, SAEs, and new treatments that come available.

Clinical Laboratory Abnormalities. Laboratory abnormalities without clinical significance are not recorded as AEs or SAEs. However, laboratory abnormalities that require medical or surgical intervention or lead to investigational medicinal product interruption or discontinuation must be recorded as an AE, as well an SAE, if applicable. In addition, laboratory assessments that are associated with signs and/or symptoms must be recorded as an AE, or SAE, if applicable. If the laboratory abnormality is part of a syndrome, record the diagnosis (i.e. anemia), not the laboratory abnormality (i.e. decreased hemoglobin).

Adverse Events. The investigator, or sub-investigator, is responsible for assessing AEs and SAEs for causality and severity. AEs will be graded using the Common Terminology Criteria for Adverse Events (CTCAE) Version 4.03. This grading scale can be found at https://evs.nci.nih.gov/ftp1/CTCAE/CTCAE_4.03_2010-06-14_QuickReference_8.5x11.pdf.

For AEs associated with laboratory abnormalities, the event should be graded on the clinical severity in the context of the underlying conditions. All AEs, regardless of cause or relationship, must be collected and reported in the eCRF database as instructed.

SAEs will be collected for the duration of the study. SAEs related to study drug, graft loss, or death will be reported to the lead investigators and the independent data and safety monitor within 24 hours of recognition by study staff. Stable chronic conditions that are present prior to the Pre-Transplant Day and do not worsen during the treatment period and safety follow up period are not considered adverse events.

Safety Review. When the first 10 study subjects reach treatment week 4, the lead investigators and the independent data and safety monitor will conduct a safety and efficacy review. When these subjects reach follow up week 12 (24 weeks after starting study drug), the lead investigators and the independent data and safety monitor will conduct another safety and efficacy review.

Early termination: Participants may withdraw their consent to participate in this study at any time after they sign informed consent. Principal investigators can terminate participant(s) from the study for safety concerns. Subjects who take at least one dose of study drug and do not complete the planned 12 weeks of treatment will come for an early end of treatment visit.

STATISTICAL CONSIDERATIONS

Analysis Objectives

The primary objective of this study is to determine the efficacy of SOF/VEL in viral eradication among HCV negative liver and/or kidney transplant recipients with HCV NAT positive donors.

The secondary objective of this study is to determine the safety and tolerability of all SOF/VEL among HCV negative liver and/or kidney transplant recipients with HCV NAT positive donors.

The exploratory objective of this study is to compare the observed waiting time for transplant for HCV negative liver and/or kidney transplant recipients with HCV NAT positive donors to the expected waiting time for transplant with HCV negative donors at the participating centers.

Primary Efficacy Endpoint

The proportion of participants with SVR 12 defined as HCV RNA < lower limit of quantification 12 weeks after last dose of antiviral therapy.

Secondary Endpoints:

- Proportion of subjects with SVR24 defined as HCV RNA < lower limit of quantification 24 weeks after last dose of antiviral therapy;
- Proportion of subjects with viral relapse defined as HCV RNA <LLOQ at end of treatment with subsequent quantifiable HCV RNA;
- Proportion of participants with on-treatment virologic breakthrough defined as > 1 log increase in viral RNA after treatment week 1;
- Proportion of subjects who prematurely discontinue antiviral therapy before the planned end of treatment;
- Patient and graft survival at 6 months post-transplant.

Exploratory Endpoint

Change in wait time for kidney and/or liver transplant based on UNOS data for the participating regions.

Analysis Sets

The primary analysis set for safety and efficacy analyses includes all subjects who undergo liver and/or kidney transplant after signing Part 2 of the Informed Consent. Treatment-emergent data will be analyzed and defined as data collected from the first dose of study drug through the date of the last dose of study drug plus 30 days.

Data Handling Conventions

Missing data will not be imputed other than for quantitative HCV PCR. If a quantitative PCR is missing, the value will be imputed as LLOQ if the viral load before and after are both LLOQ.

Efficacy Analysis

Primary and Secondary Endpoints

No formal hypothesis testing will be performed, as this is an exploratory study. No inferential statistics or statistical comparisons are planned for efficacy endpoints. All subjects who undergo liver and/or kidney transplant with a nucleic acid test positive organ will be included in the analysis. We assume that none of the subjects will achieve SVR 12 without any antiviral therapy. The existing data for SOF/VEL have demonstrated a SVR rate above 94% in non-cirrhotic patients. We anticipate a similar SVR rate for our study. Along with the percentage of patients with SVR12, a two-sided 95% confidence interval (CI) is constructed by using the Clopper-Pearson method. With a sample size of 30 patients, if the SVR12 rate is 90%, the lower bound of the 95% CI would be 79% and the upper bound of the 95% CI would be 100%.

Exploratory Endpoint

Shorter wait time from listing to transplant is a potential benefit of accepting a HCV positive organ. To characterize wait time among HCV positive organ recipients, mean wait time in log₁₀ days will be calculated separately for liver and kidney transplant recipients. With a sample size of 10, 15, or 20 patients per HCV positive organ type and a standard deviation of 1 log₁₀ days of wait time, we have 80% power to obtain a two-sided 95% CI half-width of 8, 5, and 4 days, respectively (CI half-width of 0.9, 0.7, and 0.6 log₁₀ days).

To explore wait time by acceptance of HCV positive versus negative organs, wait time would be collected for the HCV positive organ recipient and the next HCV negative organ recipient at the transplant center, matched on blood type, gender, and transplant MELD (+/-5) for liver recipients and KDPI (+/- 0.25) for kidney recipients. Mean wait time in log₁₀ days for a HCV positive versus negative organ would be compared separately among liver and kidney recipients. We anticipate obtaining wait time on 60 transplant recipients (at least 20 liver and 20 kidney recipients). For a two-sided paired t-test assuming an alpha level of 0.05, we estimate having 80% power to detect a mean difference in wait time of 20, 10, and 8 days for sample sizes of 20, 30, and 40 patients, respectively.

Safety Analysis

Safety will be assessed during the study through the reporting of AEs and by clinical laboratory tests at various time points during the study. Concomitant medication usage will also be assessed throughout the study. Descriptive statistics on the number and types of AEs will be recorded and presented in a tabular format. Treatment-emergent AEs (TEAEs) will also be summarized by relationship to study drug and severity. In addition, TEAEs leading to premature discontinuation of the study drug will be summarized and listed. Liver or kidney grade 3 or 4 laboratory abnormalities will be described in the narrative.

Independent Data and Safety Monitor (IDSM)

An IDSM with relevant clinical expertise will be chosen who has no financial, scientific,

or other conflict of interest with the trial. The IDSM will review the progress of the study, perform interim review of safety data, and provide recommendations whether the nature, frequency, and severity of AEs associated with the study warrant the early termination of the study in the best interests of the participants, whether the study should continue as planned, or the study should continue with modifications. The IDSM will also consider factors external to the study when relevant information becomes available, such as scientific or therapeutic developments that may have an impact on the safety of the participants or the ethics of the trial. When the first 10 study subjects reach treatment week 4, the lead investigators and the IDSM will conduct an open safety and efficacy review. When these same subjects reach follow up week 12 (24 weeks after starting study drug), the lead investigators and the IDSM will conduct another open safety and efficacy review. The IDSM will make recommendations to the lead investigators, and, if required, to the Food and Drug Administration concerning continuation, termination, or other modifications of the trials based on the observed beneficial or adverse effects of the treatment under study.

RESPONSIBILITIES

Investigator Responsibilities

The Principal Investigators will be responsible for recruiting study personnel, obtaining REB/IRB approval, ensuring clinic staffs are informed about the study, and supervising study activities. The study personnel will be responsible for: identifying participants, obtaining informed consent, confirming eligibility, monitoring compliance, conducting study visits, ensuring subjects have regular follow-up, encouraging attendance at visits, and collecting subject data.

Study-wide coordination

The Lead Investigators will be responsible for:

1. Holding periodic meetings to update the study group regarding enrollment, study conduct, and potential safety issues that may affect the patient's decisions about enrolling or continuing study drug throughout the study;
2. Conducting safety reviews with the IDSM after the first 10 subjects reach treatment week 4, and after the first 10 subjects reach Follow Up week 12;
3. Distributing the recommendations from the safety reviews to all co-investigators and IRBs associated with the study;
4. Supervising data management and analysis.

Quality Control and Assurance

It is the responsibility of the Principal Investigators to ensure the quality of computerized data for this study. Information documents will be specifically developed and the data will be collected securely. For each subject consented, an electronic case report form (eCRF) will be completed by an authorized study staff member. eCRFs should be completed on the day of the subject visit. The eligibility criteria eCRF should be completed only after all data related to eligibility have been received. Investigators will ensure that entries accurately reflect the information in the source documents. The site coordinator is responsible for responding to queries in a timely manner and providing reasons for updates, as needed. All records will be kept in a secure location and will only be available only to the study investigators and assigned research staff. Center specific research ethics approval will be obtained before initiating the study at that center.

Ethical Considerations

ICH Guidance E6: Good Clinical Practice: Consolidating Guideline/ Declaration of Helsinki

The conduct of this study will conform to the International Conference for Harmonization and Good Clinical Practice (ICH-GCP) regulations and guidelines and the current revision of the Declaration of Helsinki and reflected in *a priori* approval by

all the study centers' institutional review boards.

Research Ethics Board/ Institutional Review Board

A copy of the protocol (including protocol amendments), all versions of the informed consents, other information to be completed by subjects such as questionnaires, and any proposed advertising/ recruitment materials will be reviewed and approved by the center's REB/IRB prior to implementation of the study. The investigator will notify the REB/IRB of violations from the protocol and serious adverse events.

Informed Consent Process

The informed consent process for this trial is comprised of three steps:

1) Pre-screening: As part of pre-transplant evaluation, treating nephrologists and hepatologists will have a detailed discussion with their HCV negative patients regarding high-risk donors, including those who are HCV NAT-positive. For patients who express interest in receiving an HCV NAT-positive donor, their treating hepatologist or nephrologist will refer them to the principal investigator or co-principal investigator for this study.

2) Informed Consent: The principal investigator or co-principal investigator will review the potential risks and benefits of participating in this trial, including a discussion regarding HCV treatment and complications of unsuccessfully treated post-transplantation HCV, including graft loss, fibrosing cholestatic hepatitis, cirrhosis and death. The discussion will also describe that organ donors in the trial might be classified as Public Health Service elevated risk for window infection with HIV. This step of the informed consent process will include documentation that each of these elements has been reviewed with the patient who understands and has ample opportunity to have all of their questions and concerns addressed. Part 1 of the informed consent, describing in detail the study procedures, anticipated benefits and potential risks, will be given to each participant and written documentation of informed consent is required prior to starting the study. Subjects must voluntarily sign and date Part 1 of the informed consent document that has been approved by a participating center's REB/IRB prior to any procedures being done specifically for the trial. Each subject should have sufficient opportunity to discuss the study and consider the information in the consent process prior to agreeing to participate. Subjects may withdraw consent at any time during the course of the trial. The informed consent will be signed and dated by the subject, the person who conducted the informed consent discussion and the investigator. The original signed informed consent form will be retained in the subject's study files and a copy will be provided to the subject. Participants who are deemed eligible and sign consent will be rendered eligible for HCV-viremic kidney or liver offers through an opt-in mechanism in the allocation system administered by the Organ Procurement and Transplantation Network/United Network for Organ Sharing (OPTN/UNOS).

3. Confirmation of Consent: Eligibility and subject's willingness to proceed with an HCV-positive donor will be re-confirmed and documented by study staff within 24 hours of the planned liver or kidney transplant (the "Pre-Transplant day") with a review of the potential risks and benefits of participating in this trial, including a discussion regarding HCV treatment and complications of unsuccessfully treated post-transplantation HCV, including graft loss, fibrosing cholestatic hepatitis, cirrhosis and death. This step of the informed consent process will include documentation that each of these elements has been reviewed with the patient who understands and has ample opportunity to have all of their questions and concerns addressed. Part 2 The consent the patient originally signed will be presented to the patient to review and sign the Confirmation of Consent section at the bottom of the informed consent and written documentation of informed consent is required prior to proceeding with the study. Subjects must voluntarily sign and date the Confirmation of Consent section of the informed consent document that has been approved by a participating center's REB/IRB prior to proceeding with the trial. Each subject should have sufficient opportunity to discuss the study and consider the information in the consent process prior to agreeing to participate. Subjects may withdraw consent at any time during the course of the trial. The informed consent will be signed and dated by the subject, the person who conducted the informed consent discussion and the investigator. The original signed informed consent form will be retained in the subject's study files and a copy will be provided to the subject.

Virologic Failure Substudy. In the event of virologic failure following treatment with SOF/VEL, subjects will be eligible for re-treatment with 12 weeks of sofosbuvir/velpatasvir/voxilaprevir (SOF/VEL/VOX) VOSEVI therapy in the Virologic Failure Substudy. The principal investigator or co-principal investigator will review the potential risks and benefits of participating in this Substudy, Subjects will sign a separate consent form for the Virologic Failure Substudy. These subjects must complete their Day 1 visit in the Virologic Failure Substudy within 30 days of documentation of virologic failure in the main study.

Participant Confidentiality

All subject related information including the consent, laboratory samples, evaluation forms, reports, etc. will be kept strictly confidential. All records will be kept in a secure, locked location and only research staff will have access to the records. Subjects will be identified only by means of a coded number specific to each subject, and a subject letter code. All computerized databases will identify subjects by numeric codes only, and will be password protected. Upon request, clinical information may be reviewed by or released to auditors or regulatory agencies.

Record Retention

Data and study documents at all sites will be stored securely for at least 2 years after completion of the study per FDA requirements (with the specific length of time according to the site's specific requirements), after which they will be destroyed in keeping with

the privacy and confidentiality regulations and guidelines. Samples collected will be retained for at least 2 years after completion of the study (with the specific length of time according to the site's specific requirements), after which they will be destroyed.

Protocol violations and deviations

Protocol violations or deviations will be reported to the Principal Investigator and Lead Investigators. Protocol exemptions, violations, and deviations will be logged.

REFERENCES

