The primary efficacy endpoint is the proportion of subjects who achieve a sustained virologic response (SVR12). Secondary endpoints include proportion of subjects who achieve SVR24, the proportion of subjects with viral relapse or viral breakthrough and patient and graft survival at Week 36 (24 weeks after starting study drug).

Safety:

Safety will be assessed through the reporting of adverse events and clinical laboratory tests

When the first 10 subjects reach treatment week 4, the lead investigators and the independent data and safety monitor will conduct a Safety Review. When these same subjects reach follow up week 12 (24 weeks after starting study drug), the lead investigators and the independent data and safety monitor will conduct another Safety Review.

Statistical Methods:

Sample size was selected to provide safety and efficacy data. The small size of the pilot study does not permit hypothesis testing. Descriptive statistics on the number and types of AEs will be recorded and presented.

Safety Analysis:

Safety analysis will include summaries of AEs and laboratory evaluations

BACKGROUND AND SCIENTIFIC RATIONALE

In the United States, the number of patients listed for solid organ transplant dramatically exceeds the numbers of organs available and utilized for donation. For kidney transplant, mean waiting times are measured in years. There is a 4 % mortality on the kidney wait list, with much higher rates for diabetic and elderly candidates. On the liver wait list, the mortality rate is considerably higher, averaging about 20% at most centers. Numerous strategies are utilized to expand the standard donor pool for kidney or liver transplant, including using organs from deceased donors exposed to chronic viral infections (e.g. cytomegalovirus and hepatitis B virus), Public Health Services increased risk donors, older donors, donation after cardiac death, and livers with increased steatosis.

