Objective #3: To compare the observed waiting time for transplant for HCV negative liver and/or kidney transplant recipients with HCV nucleic acid test (NAT) positive donors to the expected waiting time for transplant with HCV negative donors in participating regions.

Hypothesis: Receiving a NAT positive liver and/or kidney substantially shortens the wait time for liver and/or kidney transplant.

STUDY DESIGN

Description

This is a prospective multicenter, open-label, proof of concept study being conducted at up to 6 American sites (See Appendix 2). The study aims to enroll up to 30 study subjects undergoing liver and/or kidney transplantation, at least 10 of them undergoing liver transplant and at least 10 undergoing kidney transplant.

Potential study candidates will be identified through the active wait-list for liver or kidney transplant at each participating institution. The informed consent process for this trial is comprised of three steps:

1) Pre-screening: As part of pre-transplant evaluation, treating nephrologists and hepatologists will have a detailed discussion with their patients regarding high-risk donors, including those who are HCV NAT-positive. For HCV negative patients who express interest in receiving an HCV NAT-positive donor, their treating hepatologist or nephrologist will refer them to the principal investigator or co-investigator for this study.

2. Informed consent: the principal investigator, or co-investigator, will review the potential risks and benefits of participating in this trial, including a discussion regarding HCV treatment and complications of unsuccessfully treated post-transplantation HCV, including graft loss, fibrosing cholestatic hepatitis, cirrhosis and death. The discussion will also describe that organ donors in the trial might be classified as Public Health Service elevated risk for window infection with HIV. This step of the informed consent process will include documentation that each of these elements has been reviewed with the patient who understands and has ample opportunity to have all of their questions and concerns addressed. Participants who are deemed eligible and sign consent will be rendered eligible for HCV-viremic kidney or liver offers through an opt-in mechanism in the allocation system administered by the Organ Procurement and Transplantation Network/United Network for Organ Sharing (OPTN/UNOS).

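### The synopsis rules out hypothesis testing without exception, yet wait time is given a paired t-test at alpha 0.05 with an 80% power claim, in days, that the design does not deliver

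*Combined protocol and SAP*

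**What the plan says.** Four places in the combined protocol and SAP bear on this.

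- **Synopsis, Statistical Methods.** "The small size of the pilot study does not permit hypothesis testing". The reason given is size, and no endpoint is excepted. The synopsis lists the wait-time comparison as its third objective.
- **Objectives, Objective #3.** The stated hypothesis is directional: "Receiving a NAT positive liver and/or kidney substantially shortens the wait time for liver and/or kidney transplant". The Analysis Objectives section gives the comparison exploratory status: "The exploratory objective of this study is to compare the observed waiting time for transplant".
- **Efficacy Analysis, Primary and Secondary Endpoints.** "No formal hypothesis testing will be performed, as this is an exploratory study". The next sentence sets the scope: "No inferential statistics or statistical comparisons are planned for efficacy endpoints".
- **Efficacy Analysis, Exploratory Endpoint.** Each recipient of an HCV positive organ is matched to the next recipient of a negative organ at the centre. Mean log10 wait is compared separately for liver and kidney. The section then says "For a two-sided paired t-test assuming an alpha level of 0.05" and claims "80% power to detect a mean difference in wait time of 20, 10, and 8 days for sample sizes of 20, 30, and 40 patients".

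The section gives an SD of 1 log10 day, but for the one-sample confidence interval. It gives no SD of paired differences and no within-pair correlation. Nothing says how a non-significant result would be read.

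**The concern.** A study described as too small to test anything has a named test with sidedness, alpha and power, to be run in subsets of as few as 10 pairs. A sponsor cannot follow both statements, and the plan does not say which governs.

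The power claim matters more than the inconsistency. A reader told that the comparison can detect a difference of 8 to 20 days would take a non-significant result as strong evidence against a substantial shortening of the wait. If the true power for a realistic benefit is low, that inference would be unsafe, and the published plan would appear to support it.

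**Working it through.** **Inputs.** Two-sided alpha 0.05, 80% power, SD 1 log10 day, and 20, 30 and 40 patients (Exploratory Endpoint section). The plan expects 60 recipients in total, which is 60/2 = 30 pairs, with at least 20 recipients (10 pairs) per organ. The three sample sizes are therefore 10, 15 and 20 pairs. The kidney medians of 469 and 856 days come from Background and Scientific Rationale.

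**1. Where 20, 10 and 8 come from.** The usual normal approximation for two independent groups of n, with SD 1 log10, gives a detectable difference of (1.960 + 0.842) × √(2/n).

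| n | Difference (log10) | Rounded | Antilog of rounded value | Plan states |
|---|---|---|---|---|
| 10 | 1.25 | 1.3 | 20 | 20 days |
| 15 | 1.02 | 1.0 | 10 | 10 days |
| 20 | 0.89 | 0.9 | 8 | 8 days |

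The figures reproduce, but a difference of logs back-transforms to a ratio. They mean 20-, 10- and 8-fold differences in geometric mean wait.

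**2. The same figures under the test that is named.** For n pairs with mean log10 difference δ, the paired t statistic is noncentral t with n − 1 degrees of freedom and noncentrality δ√n / SDd. Here SDd is the SD of the paired differences. With SD 1 per recipient and within-pair correlation ρ, SDd = √(2(1 − ρ)). Uncorrelated pairs give 1.41, and ρ = 0.5 gives 1.0.

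| Pairs | Ratio | Power, SDd 1.41 | Power, SDd 1.0 |
|---|---|---|---|
| 10 | 20 | 74% | 95% |
| 15 | 10 | 72% | 95% |
| 20 | 8 | 77% | 97% |

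Neither column gives 80%. The stated figures match an unpaired approximation and not the paired t-test.

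**3. The figures taken literally as days.** Around an 856-day wait, 20 days is log10(856/836) = 0.010, 10 days is log10(856/846) = 0.005, and 8 days is log10(856/848) = 0.004. With 10, 15 and 20 pairs respectively, power is about 5% at every SDd from 0.3 to 1.41. That is essentially the type I error rate.

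**4. The only effect size in the documents.** 856/469 = 1.83 and log10(1.83) = 0.261, treating the ratio of medians as a geometric mean ratio. The SDd values are assumptions.

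| SDd (log10) | 10 pairs | 15 pairs | 20 pairs |
|---|---|---|---|
| 1.41 | 8% | 10% | 12% |
| 1.0 | 11% | 16% | 20% |
| 0.5 | 32% | 47% | 60% |
| 0.3 | 69% | 88% | 96% |

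If each recipient's SD is the plan's 1 log10, then ρ = 1 − SDd²/2. An SDd of 0.5 needs a correlation of 0.875, and 0.3 needs 0.955. For 80% power the pairs required are 117 at SDd 1.0, 31 at 0.5 and 13 at 0.3.

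**5. What an interval would show.** The 95% CI half-width on the log10 scale is t(0.975, n − 1) × SDd/√n. For 10 pairs this is 2.262 × 1.0/3.162 = 0.715 at SDd 1.0, and 2.262 × 1.414/3.162 = 1.012 at SDd 1.41. The ratio would be known to within times/divide 5.2 and 10.3 respectively.

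**The case against.** **The SAP text and the t-test can stand together.** A reader might infer that the SAP repeats the synopsis and also bars this test. The documents do not support that. The SAP's no-testing sentence sits under the primary and secondary endpoints and gives exploratory status, not size, as its reason. The following sentence restricts the bar to efficacy endpoints. Wait time has its own heading. This objection stands, and the conflict is between the synopsis and the Exploratory Endpoint section.

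**The synopsis sentence may have been meant more narrowly.** It follows a statement that the sample size was chosen for safety and efficacy data, and the synopsis gives no wait-time endpoint or analysis. That is a fair reading of intent, but the sentence carries no such limit and the synopsis lists the objective.

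**No misleading conclusion is planned.** The comparison is exploratory and conditionally worded, and the t-test appears only in the power statement. No p-value reporting rule and no conclusion of no difference is written down. This stands: the misreading is a risk created by the power claim, not something the plan commits to.

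**The power range depends on an unknown SD.** A reader might infer that a non-significant result is 80% to 92% likely if the cited benefit is real. That holds only for kidney and only for SDd of 1.0 to 1.41. Pairs share a centre and are matched on blood type, gender and MELD or KDPI, so a smaller SDd cannot be excluded. The documents give no liver effect at all.

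**A 95% CI carries the same information as the test.** It does: the interval excludes a ratio of 1 exactly when p is below 0.05. Replacing the p-value alone would be preference. The unit error and the unsupported 80% are not.

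**Conclusion.** The concern holds in a limited form. The synopsis and the Exploratory Endpoint section contradict each other on whether anything is tested. Separately, the 80% power statement is wrong as written. Its days are fold ratios, and power for differences of that many days around an 856-day wait is about 5%. Even read as ratios, the named test has 72% to 77% power with uncorrelated pairs, and would exceed 80% if SDd were 1.0.

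For the cited 1.83-fold kidney difference, power runs from 8% (10 pairs, SDd 1.41) to 96% (20 pairs, SDd 0.3). At the plan's own SD of 1 log10 with correlation 0 to 0.5, it is 8% to 20%. These figures assume that the ratio of medians stands in for a geometric mean ratio, and that log waits are roughly normal. No statement about liver can be made from the documents.

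The consequence is small. The endpoint is exploratory, and neither the SVR12 analysis nor the safety analysis is touched.

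**What to change.** In the Exploratory Endpoint section:

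1. Delete the sentence giving alpha and 80% power to detect 20, 10 and 8 days. Alternatively, restate it as a detectable ratio for the paired test, with the SD of paired differences stated and justified.
2. Report the paired ratio of geometric mean wait times with its 95% CI, separately for liver and kidney, labelled exploratory and descriptive.
3. Give the expected CI width as the precision statement, for example about times/divide 5 to 10 with 10 pairs at SDd 1.0 to 1.41.

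Dropping the test in this way brings the section into line with the synopsis. If the sponsor prefers to keep the test, limit the synopsis sentence to the efficacy and safety endpoints. In that case still correct the power statement, and say that a non-significant result is not evidence of no difference.

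The cost is a wording change, with the same data and the same matched pairs. The sponsor gives up an exploratory p-value and a favourable-looking power figure.
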